4.6.3. Safety summary of Phase 2 MS trial (MN-166-CL-001)

In a Phase 2 trial conducted in CEE in RRMS patients, subjects were treated with either placebo or MN-166, 30 or 60 mg/d up to two years. Enrolled subjects received study drug for 12 months in the “core period” and if eligible, continued to the “extension period” for an additional 12 months of treatment. A total of 297 subjects were enrolled, 103 subjects were randomized to placebo group, 95 subjects were randomized to the 30 mg/d group and 99 subjects were randomized to the 60 mg/d group. Two-year completion of the 60 mg/d group was 86%.

Core period (12 m) 1 st year	# of enrolled subject	Extension period (12 mo) 2 nd year	# of enrolled subjects

CONFIDENTIAL

	(N)		(N)
Placebo	103	P-30mg	49
		P-60mg	48

During the 12-month double-blind core-period, the adverse events most frequently reported (> 5%) occurred in the SOCs of Infections and Infestations (36%), Nervous System Disorders (19%), Gastrointestinal Disorders (15%), Psychiatric Disorders (13%), General Disorders and Administration Site Conditions (9%), and Musculoskeletal and Connective Tissue Disorders (7%). No significant differences in TEAEs by SOC were observed between treatment groups. There was a slight dose related increase in the percent of subjects with gastrointestinal AEs: 8%, 12%, and 15% for placebo, 30 mg/d, and 60 mg/d treatment groups, respectively.

During the core-period, more treatment-related TEAEs were experienced by subjects in the 60 mg/d group (26 TEAEs) compared to the 30 mg/d (18 TEAEs) or placebo group (12 TEAEs). The most common treatment-related AEs were headache (n =3) and nausea (n =2) in the 30 mg/d; nausea (n =4), headache (n =3), vomiting (n=2) and dizziness (n =2) in the 60 mg/d group; and upper respiratory infection (n =5) and headache (n =2) in the placebo group.

During the 12-month open-label extension period, five additional treatment-related TEAEs occurred. These TEAEs were night cramps (1 subject 60 mg/d), hepatotoxicity (1 subject 60 mg/d), depression (1 subject 60 mg/d), and pruritus (2 subjects in placebo to 60 mg/d).

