	80 mg single dose N =9	80 mg fastin g single dose N =8	100 mg single dose N =9	Placebo N=15	80 mg (2d) -100 mg (8d) total 10 days		Placebo		60 mg (2d) 80 mg (12d) total 14 days N =16	Placebo N =10	80 mg x 14 days N =10	Placebo N =10
				HV N =9	DM N =9	HV N =3	DM N =3					
Nausea	-	1/8	3/9	-	-	1/9	-	-	5/16	1/10	1/10	2/10
Dyspepsia	-	-	-	-	-	4/9	-	-	-	-	-	-
Diarrhea	-	-	-	-	-	3/9	-	1/3	1/16	-	-	-
Vomiting	-	-	-	-	-	1/9	-	-	-	-	1/10	2/10
GI upset	-	-	-	-	-	-	-	-	-	-	2/10	4/10
Headache	1/9	1/8	1/9	3/15	2/9	3/9	1/3	-	4/16	3/10	2/10	-
ALT/AST elevation	-	-	-	-	-	1/9	-	-	-	-	-	-

[figure not shown]
*AV411-OWA study: TRAEs during double-blind phase (Weeks 2 and 3)

	MN-166 (ibudilast) related frequently observed AEs (GI symptom, Headache, Lab changes) in 80-100 mg/d regimen; completed & ongoing study						
	IBU-002-MOH		UCLA-Meth Ph1 CO*		AV411-SA CO*	UCLA Alcohol abuse CO*	UCLA Meth Ph2
	80 mg/d N=15	Placebo N=19	100 mg/d phase N=11	Placebo phase N=11	100 mg/d and Placebo	100 mg/d and Placebo	100 mg/d or Placebo
Nausea/ GI upset	10/15	2/19	4/11	4/11	Ongoing No SAE	Ongoing No SAE	Ongoing No SAE
Diarrhea	2/15	-	-	-			
Vomiting	-	-	-	-			
Headache	4/15	2/19	5/11	3/11			
ALT/AST elevation	=	=					
GGT elevation	=	6-fold UNL @ 2weeks					
Withdrawn from study	2/15 1:Unable to attend remaining study visit 1:worsening pre-exist headache	2/19 1: worsening headache 1: withheld study for GGT elevation No longer meet IC when resolved					

*study is cross-over design

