$$[a_{ih} \ b_{ih}]^T \sim \mathcal{N}(\mathbf{0}, \mathbf{G}), [a_h \ b_h \ c_h \ d_h]^T \sim \mathcal{N}(\mathbf{0}, \mathbf{H}), \epsilon_{ij} \sim \mathcal{N}(0, \sigma^2 \mathbf{I}_i), \text{ and } [a_i \ b_i]^T \perp [a_h \ b_h \ c_h \ d_h]^T \perp \epsilon_{ij}.$$

If individual site variance components in \mathbf{H} are negligible, then the associated random effects will be omitted to simplify the model. In the case that all \mathbf{H} components are negligible, we will revert to Equation (1) for the analysis.

Primary Objective #2: To evaluate the safety and tolerability of ibudilast versus placebo.

The main assessment of safety will involve a comparison of treatment-related SAEs across the two treatment groups. This will be assessed in two ways. First, the percentage of subjects who experience any treatment-related SAE in each group will be compared using a chi-square test. Then, the rates of treatment-related SAEs in each group will be compared using a Poisson regression model. We will also assess the values of laboratory assessments over time across the two groups using a LMM. To assess tolerability, the percentage of subjects who complete the entire treatment period will be compared across the two groups using a chi-square test. Appropriate constraints for baseline imbalance will be used in all statistical models.

Major Secondary Objectives: *To evaluate the activity of ibudilast at two years versus placebo, as measured by:*

- (1) *Diffusion tensor imaging (DTI) in descending pyramidal white matter tracts*
- (2) *Magnetization transfer ratio (MTR) imaging in normal-appearing brain tissue*
- (3) *Retinal nerve fiber thickness as measured by optical coherence tomography (OCT)*
- (4) *Cortical atrophy as measured by cortical longitudinal atrophy detection algorithm (CLADA)*

The secondary objectives will be analyzed using a model similar to that described above for the assessment of BPF. An exception is the OCT analysis will require additional random effects for eyes nested within patients. Additional details are provided below. The baseline intercepts will again be constrained to be equal to account for baseline imbalance.

Other Objectives

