7.2.1 Safety

The primary assessment of safety will compare the percentage of subjects in each group with:

- Treatment-emergent adverse events (TEAEs)
- Treatment-emergent serious adverse events (TESAEs)

The main assessment of safety and tolerability will involve a comparison of treatment-related AEs and SAEs across the two treatment groups. First, the percentage of subjects who experience any treatment-related AE in each group will be compared using the following logistic regression model:

$$\text{logit}(Y_i) = \beta_0 + \beta_1 x_{1i} + \beta_2 x_{2i} + \beta_3 x_{3i} + \epsilon_i$$

where

- Y_i represents an indicator of whether or not i^{th} subject had at least one treatment related AE.
- $x_{1i} = 1$ if i^{th} subject was thought to be receiving immunomodulation therapy at randomization (IFN/GA), and 0 if the subject was not thought to be receiving immunomodulation therapy
- $x_{2i} = 1$ if i^{th} subject was thought to have primary progressive MS at randomization, and 0 if the subject was thought to have secondary progressive MS
- $x_{3i} = 1$ if i^{th} subject was randomized to the Ibudilast group, and 0 if the subject was randomized to placebo group
- ϵ_i is random error for the i^{th} subject

To determine if the percentage of subjects having any treatment related AEs differ across treatment group we will test the following hypothesis:

$$H_0: \beta_3 = 0 \text{ vs. } H_A: \beta_3 \neq 0$$

If the null hypothesis is rejected, and $\beta_3 > 0$, we will conclude that Ibudilast was responsible for a significantly greater frequency of treatment-related AEs. Similarly, if $\beta_3 < 0$, we will conclude that Ibudilast was responsible for a significantly lower frequency of treatment-related AEs. In addition to an overall comparison, this hypothesis will be repeated for assessing the percentage of subjects having at least one treatment-related AE within each MedDRA system organ class (SOC). If there are significant differences between groups within any specific SOC, then additional tests will compare differences across groups for specific MedDRA preferred terms in order to further explore the cause of the observed differences.

In addition to the comparison of percentages in the manner described above, the rates of treatment-related AEs in each group will be compared using the following Poisson regression model:

$$\log\left(\frac{Y_i}{T_i}\right) = \beta_0 + \beta_1 x_{1i} + \beta_2 x_{2i} + \beta_3 x_{3i} + \epsilon_i$$

where

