The analysis used the proposed time points of 0, 24, 48, 72, and 96 weeks. Power curves were computed for DS1, DS2, and for their average (Avg). Avg was based on averaging the LMM parameter estimates across the data sets (e.g., average slope = [DS1 slope + DS2 slope] / 2). Avg was an attempt to pool information from the two data sets without the raw data (the raw data for DS2 was unavailable). A 10% dropout rate was assumed and all estimated sample sizes were inflated by this percentage (i.e., final sample size = initial sample size \times 1.10). Given the resources required for obtaining and analyzing 3T scans, the type I error rate was set at $\alpha = 0.10$. Figure 7.1 shows power curves for the three smallest effect sizes (30%, 35%, and 40%). Focusing on Avg for the middle effect size (35%), the figure indicates that a single-arm $N / 2 = 125$ provides close to 80% (power = 0.80 is the horizontal dashed line). The middle effect size is important as it nearly corresponds to the upper effect size of the aforementioned Ibudilast study (effect size = 36%). The Avg data source is preferred because it approximates a pooling of the information from both samples. The feasibility of $N / 2 = 125$ as the single-arm sample size was examined by calculating power for effect sizes with $\alpha = 0.10$ for all three data sources (DS1, DS2, Avg). The power by effect size curve and data source is shown in Figure 7.2. The figure clearly shows that the study has adequate power across the range of possible values suggested by these two data sources. For the “best” data (DS1), our study has slightly less than 90% power to detect effects of approximately 40% or larger, and more than 90% power to detect effects on the upper end of the range of interest (50%). Most importantly, the figure shows that the power based on the Avg data source is very high for effects in the 33% - 36% range of greatest interest (approximately 80% - 85%). Therefore, based on these assumptions, we are confident that a per-arm sample size of $N / 2 = 125$ ($N = 250$ total participants) is sufficient to help ensure statistically reliable results for the proposed study.

Figure 9.1: Power as a Function of Single-arm sample size, effect size, and data set

[figure not shown]
[figure not shown]

Figure 9.2: Power as a Function of Effect Size and data source for sample size of 125 and alpha = 0.10

9.2. Primary Objective #2: Evaluate the safety and tolerability of Ibudilast (MN-166) versus placebo

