With an overall significance level of 0.10, the study will have 80% or greater power to detect differences in safety or tolerability of 15% or greater across the two groups. Thus, minor safety concerns may not be detected in this study – and would need to be assessed in a larger, future phase 3 trial. Nevertheless, the study is adequately powered to detect major safety concerns.

9.3. Major Secondary Objective (a): Evaluate the activity of Ibudilast (MN-166) versus placebo as measured by diffusion tensor imaging (DTI) in pyramidal white matter tracts.

The power analysis was based on longitudinal DTI pilot data with the outcome measure being longitudinal diffusivity (LD) within corticospinal tracts among RRMS and SPMS starting therapy with natalizumab (Fox 2010). Eighteen MS patients were measured five times over 24 months. Equation (2) was the basis for computing required sample size based on the LMM. In order to express power $(1 - \beta)$ as a function of the fixed sample size $(N / 2 = 125)$ and the other quantities, the following equation can be used

$$1 - \beta = \Phi \left[\left(\sqrt{\frac{125 \cdot \delta^2}{\left(\sum_k \sum_l^L \mathbf{X}_{kl}^T \mathbf{V}_{kl}^{-1} \mathbf{X}_{kl} \mathbf{P}_{kl} \right)_{4,4}^{-1}}} \right) - Z_{1-\alpha/2} \right]$$

where $\Phi[\cdot]$ is the cumulative distribution function of the standard normal distribution. Estimated power was calculated using Equation (3) for the δ effect sizes discussed previously. The results show that the estimated power was greater than 0.90 for the smallest effect size (30% difference in slopes). This result implies that $N = 250$ patients is sufficient to provide high power for testing the equality of LD slopes in the treatment and control groups for the range of plausible effect sizes that is anticipated in the proposed study.

9.4. Major Secondary Objective (b): Evaluate the activity of Ibudilast (MN-166) versus placebo as measured by magnetization transfer ratio (MTR) imaging in normal appearing brain tissue.

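### The stated 80% or greater power for a 15-point safety or tolerability difference sets no condition on the event rate; with the planned two-sided 0.10 tests it falls to about 76-77% when the lower rate is mid-range

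*Combined protocol and SAP*

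**What the plan says.** SAP 9.2, and the Safety Objective paragraph of protocol 12.1.3 in the same words, say that at an overall 0.10 level "the study will have 80% or greater power to detect differences in safety or tolerability of 15% or greater across the two groups". Both then say that minor safety concerns may be missed but that the study is adequately powered for major ones. No event rate, formula or sidedness is given.

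The planned tests are stated elsewhere. In protocol 12.1.2, "the percentage of subjects who experience any treatment-related SAE in each group will be compared using a chi-square test"; completion of treatment is compared the same way. In SAP 7.2.1, "the percentage of subjects who experience any treatment-related AE in each group will be compared using the following logistic regression model", against the alternative that the treatment coefficient differs from zero. All treatment-emergent AEs and SAEs, and early discontinuation, are handled with similar models (SAP 7.2.1 and 7.2.2).

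On the primary endpoint, SAP 9.1 and protocol 12.1.3 say that for the averaged pilot parameters at 35% slowing, 125 per arm "provides close to 80% (power = 0.80 is the horizontal dashed line"). Later in the same paragraph, power for the same source "is very high for effects in the 33% - 36% range of greatest interest (approximately 80% - 85"%). The paragraph also says: "A 10% dropout rate was assumed and all estimated sample sizes were inflated by this percentage". The synopsis gives close to 80% for effects of 33% or larger. It cites one pilot set of 36 RR and SP patients, whereas SAP 9.1 cites 30 PP patients plus 42 RR and SP patients.

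**The concern.** The safety sentence is a floor: at least 80% for every difference of at least 15 points. For fixed n and a fixed absolute difference, power depends on where the two rates lie and is lowest when they straddle 50%. A floor without a rate condition must hold there too.

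Safety and tolerability is a primary objective, and the conclusion about major safety concerns leans on this figure. The endpoints most likely to have mid-range rates over 96 weeks are the broad ones, such as any treatment-related AE or any treatment-emergent AE. For these, a reader may take a non-significant result as stronger reassurance than the design gives.

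Separately, the primary power figures do not say which of them allow for dropout, and the pilot data are described in two ways.

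**Working it through.** **Inputs.** Two-sided alpha 0.10, z = 1.645 (level from SAP 9.2; sidedness from SAP 7.2.1 and the chi-square test in protocol 12.1.2). n = 125 per arm (SAP 1). The safety population is everyone randomized and dosed (SAP 6.2), so dropout does not reduce n. Difference d = 0.15, read as absolute percentage points. The lower rate p1 is not given, so it is scanned.

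**Usual formula.** Power = Φ((d − 1.645·s0)/s1), with s0 = √(2·p̄(1−p̄)/n) and s1 = √([p1(1−p1)+p2(1−p2)]/n).

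At 42.5% vs 57.5%: s0 = √(2×0.25/125) = 0.06325 and s1 = √(0.48875/125) = 0.06253. Then (0.15 − 0.1040)/0.06253 = 0.735, and power is **76.9%**.

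**Wald approximation for the logistic model** (stratification terms ignored). Power = Φ(log OR/SE − 1.645), with SE = √(1/[n·p1(1−p1)] + 1/[n·p2(1−p2)]).

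At the same rates: log OR = 0.6046, SE = 0.2559 and the ratio is 2.363, so power is **76.4%**.

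| Lower rate | Formula | Logistic Wald |
|---|---|---|
| 4% | 98.4% | 95.9% |
| 10% | 93.4% | 91.7% |
| 14% | 89.7% | 88.3% |
| 25% | 81.6% | 80.8% |
| 28% | 80.1% | 79.4% |
| 36% | 77.5% | 77.0% |
| 42.5% | 76.9% | 76.4% |
| 57% | 80.1% | 79.4% |
| 60% | 81.6% | 80.8% |
| 70% | 88.8% | 87.5% |

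**Where it falls below 80%.** Lower rates of 28.2-56.8% by formula, 28.5-56.5% by exact enumeration of the uncorrected chi-square (minimum 77.7%), and 26.6-58.4% by logistic Wald.

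**Can the stated figure be reproduced at every rate?** Only with a one-sided 0.10 test (minimum 86.5%), which is not planned for safety.

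**What would give 80% at every rate.** At the centre, 136 per arm gives 79.9% and 137 gives 80.2%. At 125 per arm, a 15.7-point difference gives 80.2% by formula. At 16 points (42% vs 58%) the formula gives (0.16 − 0.1040)/0.06243 = 0.897, or **81.5%**. Exact chi-square gives 82.2%. Logistic Wald gives 0.6455/0.2563 = 2.519, hence **80.9%**. The Wald minima apply where at least about one event per arm is expected (rate 1/125 = 0.8% or more, and likewise at the top end). Closer to 0% or 100% the approximation breaks down; the formula still gives 99.8% for 15 points at a 0.1% rate.

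**Where might the rates lie?** The table in protocol 4.6.5 of "related frequently observed AEs (GI symptom, Headache, Lab changes) in 80-100 mg/d regimen" shows, for an 11-subject crossover study at 100 mg/d, nausea/GI upset 4/11 (36%) in both phases and headache 5/11 (45%) vs 3/11 (27%). It also shows 2/19 (10.5%) on placebo for each in the headache trial. SAE rates by dose group in the earlier MS trial were 3.9-10.1% (synopsis). On retention, "Two-year completion of the 60 mg/d group was 86"%, so about 14% did not complete.

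**Primary power.** The formula in SAP 9.1 reduces to power(e) = Φ(k·e − 1.645). From 80% at 35%, k = (0.842 + 1.645)/0.35 = 7.104. That gives 75.8% at 33% and 81.9% at 36%. Removing the 10% inflation multiplies k by √1.10 = 1.049 and gives 79.2% and 85.0%. Reading close to 80% as 82% gives 77.9% and 83.9%.

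**The case against.** The gap is small: at most 3.1 points by formula and 2.3 by exact chi-square. It does not touch the endpoints that the protocol itself names for its chi-square tests. Treatment-related SAEs should be rarer than the 4-10% SAE rates of the earlier trial, where none was judged related.

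For treatment-related AEs, the closest evidence is that trial's 12 related events among 103 placebo subjects in 12 months, so at most 11.7% of subjects. Power there is 91.8% (formula) or 90.3% (logistic Wald). Doubling the rate for two years, an assumption, gives 23.3% and still 82.5% or 81.7%. The 4/11 figures come from a tiny study in another population. All of this stands as a limit on the consequences. It does not rescue a sentence that carries no rate condition and also covers any treatment-emergent AE, whose rate is not given.

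A reader might infer that the trial is underpowered for major safety concerns. The documents do not support that: 80% is restored at about 15.7 points, and the text already concedes that minor concerns may be missed.

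A reader might also infer that the two primary power statements contradict each other. That is not established. The inflation is described as applied to sample sizes, which fits the power-by-sample-size figure, while the other figure is captioned for a sample size of 125. On that reading the stated range is reproduced, and 79.2% at 33% also agrees with the synopsis. Both statements are approximate readings of figures that are not visible in the available text.

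**Conclusion.** The safety power sentence is wrong as written, by at most 3 to 4 points, for lower rates of about 28-57% (27-58% for the logistic test). It is right outside that band, including for SAEs and for discontinuation near 14%. The arithmetic is firm given 125 per arm, a two-sided 0.10 test and 15% read as absolute points. For 120-128 per arm the exact chi-square minimum is 76.0-78.4%. Whether any actual endpoint falls in the band is an assumption.

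On the primary endpoint no error is shown. What remains is documentation. The close-to-80% and 80-85% statements fit closely only if one allows for the 10% dropout and the other does not, and the text does not say so. The pilot data also differ between the synopsis (36) and SAP 9.1 (30 plus 42), and whether the 36 are among the 42 is not stated.

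**What to change.** In SAP 9.2 and protocol 12.1.3, replace the sentence with one of the following and name the two-sided 0.10 test it refers to:

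- 80% or greater power for a 16-point difference at any event rate (minimum 81.5% by formula, 80.9% by logistic Wald); or
- about 76% or greater power for a 15-point difference at any event rate, and 80% or greater when the lower rate is below about 27% or above about 58%.

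In SAP 9.1 and protocol 12.1.3, state for each primary power figure whether it allows for the 10% dropout. Give one description of the pilot data there and in the synopsis, and say how the 36 relate to the 42. Take these labels from the existing calculation; the back-calculated values above are a consistency check and should not be printed as the study's power.

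The cost is a few reworded sentences. N and every analysis stay as they are.

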Over the entire study, a total of 20 SAEs were reported by 19 subjects. Of these 20 SAEs, 12 SAEs were reported by 12 subjects in the core period and nine SAEs were reported by 7 subjects during the extension period. More subjects in the 60 mg/d dose group (10.1%) experienced an SAE compared to the placebo to 30 mg/d (5.8%), placebo to 60 mg/d (3.9%), and 30 mg/d (4.2%) dose groups. Overall the most commonly reported SOCs for the SAEs were in Gastrointestinal Disorders and Injury, Poisoning and Procedural Complications categories. All of the SAEs were considered by the Investigators to be unlikely related or not related to study drug. Eight of the SAEs were considered by the Investigator to be severe or life threatening. No deaths occurred during the study.

A total of 9 subjects discontinued from the study due to a TEAE; two of these subjects had TEAEs that were considered to be treatment-related; hepatic steatosis in the 30 mg/d group and hepatotoxicity in the 60 mg/d group.

The safety of MN-166 from 30 to 80 mg/d has also been evaluated in single and multiple doses up to 14 days has also been evaluated in healthy volunteers and diabetes mellitus Type 1 & 2 patients and chronic pain patients (diabetic neuropathy and complex regional pain syndrome). MN-166 100 mg/d has been evaluated in single and multiple doses for up to 8 days (following 6 days of dose-incremental 40, 60 and 80 mg/d dosing at 2 days each) in healthy volunteers and diabetes mellitus Type 1 and 2 patients. A Phase 1b safety study to evaluate MN-166 in methamphetamine-dependent addicts recently completed enrollment. In this study, subjects received 40 mg/d for 1 week and then 100 mg/d for 1 week. Medication overuse headache (MOH) pain patients are currently being enrolled in a trial with dosing at 80 mg/d for 2 months and opioid addicts at 100 mg/d for 3 weeks in another trial. To date, approximately 450 subjects have been dosed with MN-166.

The Phase 2 RRMS trial results suggest that MN-166 is best positioned for primary neuroprotection in MS subjects (Fox 2010) and the dose-response data from this and other controlled neurological trials suggest that doses ≥ 60 mg/d may be ideal.

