After Day 15, subjects with intolerable side-effects (eg nausea, diarrhea, vertigo) may reduce their dose to either 4 capsules twice a day (80 mg/d for those taking ibudilast) or 3 capsules twice a day (60mg/d for those taking ibudilast). Subjects with intolerable side-effects (eg nausea, diarrhea, vertigo) at the end of Day 14 may continue to taking 3 capsules twice a day at the Investigator's discretion. At the investigator's discretion, the daily dose of ibudilast can be changed between 3 capsules twice a day, 4 capsules twice a day, and 5 capsules twice a day over the first 8 weeks of treatment. At the end of the first 8 weeks of treatment, the subject must maintain their then-current daily dose of study medication (3 capsules twice per day, 4 capsules twice per day, or 5 capsules twice per day) for the duration of the trial. Additionally, at the investigator's discretion, the daily dose of ibudilast may be divided and taken three times per day to help improve tolerability.

Subjects will return to the clinic for follow-up visits on a regular basis at Weeks 4, 8, 12, 24, 36, 48, 60, 72, 84 and 96 (see Table 1 Schedule of Assessments).

Subjects who experience a relapse will return to the clinic within three days of notifying the Investigator and will undergo assessments described in Table 2 Schedule of Unplanned Procedures and Assessments).

Subjects who prematurely discontinue study medication will continue to be followed on a semi-annual basis (Table 2 Schedule of Unplanned Procedures and Assessments) until the end of the study (Week 96).

For subjects who are no longer taking study drug and are being followed on a semi-annual basis (Wk 24, 48, 72, 96), adverse events will not be collected post study drug discontinuation. Existing AEs will be followed until the AE resolves or stabilizes.

Follow-up Phase

All subjects who complete the study active on study medication will return for a follow-up safety visit at Week 100 (4 weeks after their last study visit) to assess general health and adverse event status.

Number of Subjects (Planned): The number of randomized subjects planned for this study is 250: 125 in the placebo treatment group and 125 in MN-166 100 mg/d treatment group.

Study Entry Criteria:

Inclusion Criteria:

- Written informed consent is obtained and willing and able to comply with the protocol in the opinion of the Investigator
- Male or female subjects ages 21 to 65, inclusive

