- Y_i represents the number of treatment related SAEs experienced by the i^{th} subject.
- T_i represents the number of months between the date of randomization and the date of last follow-up for the i^{th} subject.
- $x_{1i} = 1$ if i^{th} subject was thought to be receiving immunomodulation therapy at randomization (IFN/GA), and 0 if the subject was not thought to be receiving immunomodulation therapy
- $x_{2i} = 1$ if i^{th} subject was thought to have primary progressive MS at randomization, and 0 if the subject was thought to have secondary progressive MS
- $x_{3i} = 1$ if i^{th} subject was randomized to the Ibudilast group, and 0 if the subject was randomized to placebo group
- ϵ_i is random error for the i^{th} subject

To determine if the rate of treatment related SAEs differ across treatment group we will test the following hypothesis:

$$H_0: \beta_3 = 0 \text{ vs. } H_A: \beta_3 \neq 0$$

If the null hypothesis is rejected, the direction of β_3 will indicate the direction of the observed effect. Values of $\beta_3 > 0$ indicate an increased rate of treatment-related AEs associated with the Ibudilast group, while values of $\beta_3 < 0$ indicate a decreased rate of treatment-related AEs associated with the Ibudilast group.

Treatment-related SAEs will be analyzed in the same manner described above. Additional safety analyses will also assess all treatment-emergent AEs, treatment-emergent SAEs, unanticipated SAEs, and treatment-related & unanticipated SAEs in a similar manner.

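### The claim of adequate power for major safety concerns is not supported for serious adverse events: at a control rate of about 5%, a doubling has about 46% power, and no confidence interval is planned

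*Combined protocol and SAP*

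**What the plan says.** SAP 9.2, repeated in the Safety Objective paragraph of protocol 12.1.3, makes three statements in sequence:

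- At the 0.10 level, power of at least 80% is claimed "to detect differences in safety or tolerability of 15% or greater across the two groups".
- A limit is then conceded: "Thus, minor safety concerns may not be detected in this study", and these would be left to a larger phase 3 trial.
- The paragraph ends: "Nevertheless, the study is adequately powered to detect major safety concerns".

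Neither place gives a control rate or says what counts as major.

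SAP 7.2.1 begins: "The primary assessment of safety will compare the percentage of subjects in each group with" events of two kinds, namely treatment-emergent adverse events (TEAEs) and treatment-emergent SAEs (TESAEs). Its main comparison is of treatment-related AEs and SAEs, by logistic and Poisson regression. Treatment-emergent events are then analysed similarly. The tests are two-sided: "If the null hypothesis is rejected, the direction of" the coefficient is read afterwards. Protocol 12.1.2 uses a chi-square test for the corresponding percentages.

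SAP 7.2.1 and 7.2.2 plan no risk difference and no confidence interval. SAP 7.1 plans 90% intervals for brain parenchymal fraction (BPF) and warns that failing to reject does not mean accepting the null. No such warning is attached to safety.

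**The concern.** The three sentences of SAP 9.2 use 15 percentage points, in effect, as the line between minor and major. That may be a fair target for common adverse events or for discontinuation. For SAEs it is very wide. The only SAE percentages by group in the documents are those of the earlier trial, given in the Rationale of the protocol synopsis: 5.8% and 3.9% in the two placebo-start groups and 4.2% on 30 mg/d. The same sentence reports: "More subjects in the 60 mg/d dose group (10.1%) experienced an SAE". Against a background near 5%, the plan's split would class a doubling or even a tripling of SAEs as minor.

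Safety is half of the primary objective, and protocol 4.6.5 summarises prior experience at 100 mg/d as lasting up to 8 days. A reader of the final report who sees a non-significant SAE comparison, an assurance of adequate power and no interval has nothing to show how large an increase the data still allow.

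**Working it through.** **Inputs**

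- Sample size: "125 in the placebo treatment group and 125 in MN-166 100 mg/d treatment group" (synopsis). SAP 6.2 keeps everyone who was randomized and took at least one dose, so n = 125 per arm.
- Level: two-sided 0.10, z = 1.645 (SAP 9.2 for the level, 7.2.1 for the sidedness).
- Control SAE rate: not given for this trial, so assumed and varied. The anchor is the earlier trial's placebo-start patients. The reported percentages fit 3/52 = 5.8% and 2/51 = 3.9%, which gives 5/103 = 4.9% combined. With 4/95 and 10/99, the counts sum to the 19 subjects reported. The 52/51 split is rebuilt from rounded percentages.

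**Formula** (pooled-variance normal approximation, p̄ = mean of p1 and p2)

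Power = Φ{ [√n (p2 − p1) − z √(2 p̄(1 − p̄))] / √(p1(1 − p1) + p2(1 − p2)) }

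**Step 1. The plan's own figure.** For 5% v 20%, p̄ = 0.125:

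(11.180 × 0.15 − 1.645 × 0.4677) / 0.4555 = (1.677 − 0.769) / 0.4555 = 1.99, so power is 0.98.

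The same 15 points gives 0.93 from a 10% control rate, 0.85 from 20%, 0.79 from 30%, and 0.77 at worst, near 42%. So the 80% figure holds at SAE-like rates and is only marginally short at mid-range rates. The figure is not the problem. But 20% / 5% is a fourfold risk.

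**Step 2. A doubling from 5%.** For 5% v 10%, p̄ = 0.075:

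(11.180 × 0.05 − 1.645 × 0.3725) / 0.3708 = (0.559 − 0.613) / 0.3708 = −0.145, so power is 0.44.

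Exact enumeration of the chi-square test over all pairs of binomial counts gives 0.46. A Wald logistic test without covariates gives 0.42 and Fisher's test 0.34.

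**Step 3. Range over the control rate** (exact chi-square, 125 per arm)

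| Control v drug | Power | Missed |
|---|---|---|
| 4% v 8% | 0.40 | 60% |
| 5% v 10% | 0.46 | 54% |
| 6% v 12% | 0.52 | 48% |
| 8% v 16% | 0.63 | 37% |
| 10% v 20% | 0.72 | 28% |
| 12% v 24% | 0.80 | 20% |
| 15% v 30% | 0.89 | 11% |

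A doubling is missed more often than not only below a control rate of about 5.7% (exact) to 5.9% (approximation). Power for a doubling reaches 80% only at about 12%.

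**Step 4. Detectable increase at 5%.** 80% power needs about 13.9% on drug (exact; 14.2% by the formula), a ratio of about 2.8. Detecting 5% v 10% with 80% power would need about 343 per arm.

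**Step 5. What an interval would show.** With 11 v 6 patients having an SAE (8.8% v 4.8%), chi-square p = 0.21. The difference is 4.0 points, with a Newcombe 90% interval of −1.4 to +9.6. With 6 v 6 the interval is −4.8 to +4.8, so even equal counts leave a doubling of the 4.8% rate at the limit.

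**The case against.** **The 5% rate is borrowed.** It comes from a relapsing-remitting trial in patients aged 18 to 55, and its placebo-start groups took ibudilast in year 2. This trial enrols progressive disease up to age 65 with EDSS 3.0 to 6.5, so a higher SAE rate is possible. This stands. A reader might infer that the SAE test misses a doubling more than half the time as a property of the design. The documents do not support that without the condition that the control rate is below about 5.7% to 5.9%. Nor should single contrasts from the earlier trial be used as if they were placebo comparisons: 4.2% v 10.1% compares two active doses, and 5.8% is only the higher of the two placebo-start groups.

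**No decision rule treats non-significance as safety.** This also stands. A reader might infer that a p-value above 0.10 would be taken to rule out major harm. SAP 7.2.1 states conclusions only for rejection, and SAP 9.2 concedes that some concerns may go undetected. The adequacy sentence invites that reading but does not prescribe it.

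**Safety does not rest on these tests alone.** The Medical Safety Monitor reviews each SAE in near real time (SAP 2.2) and tabulations by blinded group every quarter (SAP 10.3). The DSMB can recommend stopping (SAP 11.1), and protocol 11.1 adds clinical review of laboratory values, ECGs and examinations. These protect participants during the trial. They do not make the power statement right or supply an interval for the final comparison.

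**The SAP's main comparison is treatment-related events.** The figures above are for all-cause SAEs. No SAE in the earlier trial was judged related to drug, so related SAEs may be rarer, and power for a doubling of them would then be lower.

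**Conclusion.** The adequacy claim is not supported for SAEs. It rests on a 15-point difference which, at an assumed control rate of about 5%, is a fourfold rise. At that rate a doubling has about 46% power and 80% power needs about 14% on drug. Across control rates of 4% to 15%, power for a doubling runs from about 40% to 89%, and it is below 80% at any control rate under about 12%. These figures assume 125 per arm, a two-sided 0.10 chi-square test and all-cause SAEs. The stated 80% for 15 points is itself sound at SAE-like rates.

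This is a fault of wording and reporting. It does not show that the trial is unsafe or its monitoring deficient.

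**What to change.** 1. In SAP 9.2 and protocol 12.1.3, replace the adequacy sentence with the detectable SAE increase, its assumed control rate and the range. For example: for SAEs with a control rate of about 5%, power is 80% only for a rise to about 14%; a doubling has about 46% power at a 5% control rate, 72% at 10% and 89% at 15%.
2. Extend to the safety comparisons the caution in SAP 7.1 that failing to reject is not accepting the null.
3. In SAP 7.2.1, report the risk difference (ibudilast minus placebo) with a two-sided 90% confidence interval for TESAEs and TEAEs, beside the planned tests. Do not turn the upper limit into a decision rule: the documents give no margin, and even 6 v 6 patients gives an upper limit of +4.8 points.

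The cost is one extra table column and a less favourable statement of safety power. Sample size, data collection, case-level SAE review and DSMB monitoring are unchanged.
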